4.2 Exclusion Criteria

- Transformed CLL, including Hodgkin and non-Hodgkin lymphoma
- Active autoimmune hemolytic anemia or thrombocytopenia

- Known bleeding disorders
- Impaired hepatic function: Total bilirubin ≥ 1.5 x upper limit of normal unless due to Gilbert's disease, AST/ALT ≥ 2.5 x institutional upper limit of normal unless due to infiltration of liver, Child-Pugh class B or C
- Impaired renal function: estimated GFR < 30 ml/min/1.73m² based on CKD-EPI
- Life-threatening illness, medical condition or organ system dysfunction which, in the investigator's opinion, could compromise the subject's safety, interfere with the absorption or metabolism of ibrutinib and fludarabine, or put the study outcomes at undue risk
- Concomitant immunomodulatory therapy, chemotherapy, radiotherapy or experimental therapy
- Active Hepatitis B or Hepatitis C infection
- HIV infection
- Female patients who are currently in pregnancy, or unwilling to use acceptable methods of contraception or refrain from pregnancy if of childbearing potential or currently breastfeeding. Male patients who are unwilling to follow the contraception requirements described in this protocol.
- Psychiatric illness/social situations that would limit the patient's ability to tolerate and/or comply with study requirements.
- Unable to understand the investigational nature of the study or give informed consent.
- Individuals < 18 years old
- Known hypersensitivity to any component of ibrutinib or fludarabine
- Requires concomitant anticoagulation with Coumadin (warfarin) or other vitamin K antagonists.
- Prior malignancy, except for adequately treated basal cell or squamous cell skin cancer, in situ cervical cancer, or other cancer from which the subject has been disease-free for ≥ 2 years or which will not limit survival to < 2 years.
- Malabsorption syndrome, disease significantly affecting gastrointestinal function, or resection of the stomach or small bowel or ulcerative colitis, symptomatic inflammatory bowel disease, or partial or complete bowel obstruction.
- History of stroke or intracranial hemorrhage within 6 months before the first dose of study drug
- Major surgery within 4 weeks of first dose of study drug.

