Drug	Cycle	Condition at the start of cycle	Action*
Ibrutinib	1 and onwards	ANC <500/μL OR PLT <50,000/μL	Check CBC with differential weekly. Hold ibrutinib if cytopenia persists for ≥ 7 days OR if PLT <50,000/μL with bleeding. Resume ibrutinib when ANC ≥750/μL AND PLT ≥50,000/μL. 
 • First occurrence: Resume ibrutinib at 420 mg once daily (original dose). • Second occurrence: Resume ibrutinib at 280 mg once daily. If cytopenia does not recur after 2 cycles of ibrutinib 280 mg once daily, investigator may increase ibrutinib to 420 mg once daily.
Fludarabine	3 and 4	HGB <11 g/dL with indications of autoimmune hemolysis	Omit fludarabine.
		ANC 750 - <1,000/μL OR PLT 50,000 - <75,000/μL	Defer fludarabine and check CBC with differential weekly. Resume fludarabine at original dose when ANC ≥1,000/μL AND PLT ≥75,000/μL. If count recovery does not occur in 8 weeks, omit fludarabine.
		ANC <500/μL, OR PLT <50,000/μL	Defer fludarabine, and check CBC with differential weekly. Resume fludarabine at 20% reduced dose when ANC ≥1,000/μL AND PLT ≥75,000/μL. If count recovery does not occur in 8 weeks, omit fludarabine.

ANC - absolute neutrophil count; PLT – platelet

* Dose delay or reduction is not required if cytopenia is considered related to CLL.

5.4.2 Atrial fibrillation:

- For new-onset atrial fibrillation, ibrutinib will be held until cardiac evaluation has been completed. The decision to restart ibrutinib will be made after the PI and consulting physician determine the subject is sufficiently stable following diagnostic testing and institution of treatment if required.
- Anticoagulation with atrial fibrillation: If anticoagulation is deemed necessary by consulting physician and/or PI, patients will be allowed to start treatment with anti-platelet or anti-coagulant therapies except warfarin. Co-administration with warfarin has been associated with grade 3 or higher bleeding events such as (subdural hematoma, gastrointestinal bleeding, hematuria, and post procedural hemorrhage). Other forms of anti-platelet, anti-coagulant, direct thrombin inhibitors, or factor Xa inhibitors may be used concomitantly with ibrutinib, however the risk of increased bruising or bleeding is unknown. Patients will be counseled and monitored closely for signs of bleeding and/or bruising and will be instructed to contact the research team and primary care physician in the case of any complications.

5.4.3 Non-hematologic toxicities:

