- After a grade 3 or higher non-hematological toxicity (despite optimal supportive care) resolves, ibrutinib will be restarted as follows;

Occurrence	Action
1 st	Hold ibrutinib until recovery to Grade \leq 1 or baseline; restart at the original dose level (420mg daily).
2 nd	Hold ibrutinib until recovery to Grade \leq 1 or baseline; restart at one dose level lower (280mg daily).
3 rd	Hold ibrutinib until recovery to Grade \leq 1 or baseline; restart at one dose level lower (140mg daily).
4 th	Discontinue ibrutinib.

- A high number of circulating malignant cells ($>400,000/\mu\text{L}$) may confer increased risk; these subjects should be closely monitored. Administer supportive care such as hydration and/or leukapheresis as indicated. Ibrutinib may be temporarily held, and PI should be contacted.
- In the event that ibrutinib is withheld for a toxicity of 28 consecutive days the study drug should be discontinued. However, if clinical benefit outweighs the risk of restarting treatment then patient may restart study drug after > 28 consecutive days off study drug per PI discretion.
- For fludarabine, after a grade 3 non-hematological toxicity (despite optimal supportive care), when the toxicity resolves to grade 2 or lower and clinical benefit outweighs the risk, treatment can be restarted with 20% dose reduction on the subsequent cycle. Patients experiencing \leq Grade 2 side effects may continue treatment. Supportive measures as appropriate should be taken to minimize side effects. An interruption of study drug administration is permissible. In select cases where a subject has uncomfortable grade 2 toxicities, dose may be reduced by one dose level per PI discretion.

Dose changes must be recorded in the Dose Administration eCRF.

5.4.4 Dose modification for hepatic impaired subjects:

- Ibrutinib is metabolized in the liver and therefore subjects with clinically significant hepatic impairment at the time of screening (Child- Pugh class B or C) are excluded from study participation.
- For subjects with existing chronic mild hepatic impairment (Child-Pugh class A) at enrollment, the starting dose has to be adjusted to a level of 280 mg daily (two capsules).
- For subjects who develop mild liver impairment while on study (Child-Pugh class A), the recommended dose reduction for ibrutinib is to a level of 280 mg daily (two capsules).

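### The ibrutinib restart rules in 5.4.1 and 5.4.3 assume a 420 mg start and make no exception for subjects enrolled with Child-Pugh A impairment, who must start at 280 mg

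*Combined protocol and SAP*

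**What the plan says.** **Who can enrol.** The hepatic exclusion in 4.2 sets limits on bilirubin and AST/ALT and ends "unless due to infiltration of liver, Child-Pugh class B or C". Class A is not excluded as such, and 5.4.4 expressly provides for it.

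**Starting dose.** For class A at enrollment, 5.4.4 makes the reduction mandatory: "the starting dose has to be adjusted to a level of 280 mg daily (two capsules)". For subjects who become class A on study, 280 mg is only recommended.

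**Cytopenia, 5.4.1.** The steps are "First occurrence: Resume ibrutinib at 420 mg once daily (original dose)", then "Second occurrence: Resume ibrutinib at 280 mg once daily". If cytopenia does not recur over 2 cycles at 280 mg, the "investigator may increase ibrutinib to 420 mg once daily".

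**Non-hematologic toxicity, 5.4.3.** After a first grade 3 or higher event, "restart at the original dose level (420mg daily)". After a second, "restart at one dose level lower (280mg daily)". The third row gives 140 mg and the fourth discontinues ibrutinib.

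**Link between sections.** 5.4.4 refers acute grade 3 or higher liver-enzyme toxicity back to 5.4.3. It does not call 280 mg a ceiling and gives no reduction steps of its own for subjects who start there.

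**The concern.** The protocol lowers the start for class A because ibrutinib is cleared by the liver. Section 2.6.1 reports a 2.7-fold higher single-dose AUC in class A than with normal liver function. It also reports more grade 3 or higher reactions in mild impairment, defined there by NCI-ODWG rather than Child-Pugh criteria.

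A restart rule should return such a subject to the reduced dose or below it. The printed milligrams instead allow a higher dose than the mandated one just after a toxicity. The alternative reading leaves a repeat cytopenia without a dose reduction. At stake are the safety of a few subjects and consistent dosing between treating clinicians.

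**Working it through.** No design figure is involved, so the check sets the sections side by side for a subject who starts at 280 mg.

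**Inputs.** Mandated start 280 mg (5.4.4). Restart doses 420 and 280 mg with an optional 420 mg (5.4.1). Restart doses 420, 280 and 140 mg, then stop (5.4.3). Capsule strength 140 mg (12.1), swallowed intact (5.1).

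| Step | 5.4.1 by milligrams | 5.4.1, original = 280 | 5.4.3 by milligrams | 5.4.3 relative throughout |
|---|---|---|---|---|
| Start | 280 | 280 | 280 | 280 |
| 1st occurrence | 420 | 280 | 420 | 280 |
| 2nd occurrence | 280 | 280 | 280 | 140 |
| 3rd occurrence | not given | not given | 140 | no level left |
| 4th occurrence | not given | not given | stop | stop |
| Optional rise | 420 | 420 | none | none |

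**First restart.** By the milligrams, 420/280 − 1 = +50% in both tables. If original means the subject's own dose, the change is 0%, but the printed 420 mg then has to be ignored.

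**Second occurrence, 5.4.1.** The text is in milligrams only.
- If the first restart went to 420 mg, the cut from the current dose is (420 − 280)/420 = 33%, and the cut from the mandated start is (280 − 280)/280 = 0%.
- If the first restart stayed at 280 mg, the second cytopenia brings no cut at all.

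**Optional rise, 5.4.1.** Also in milligrams only: 420/280 − 1 = +50% over the mandated start on either reading.

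**Second and third occurrence, 5.4.3.** A consistent relative reading gives 280 and then 140 mg, a cut of (280 − 140)/280 = 50%. The third row then asks for a level below one capsule, 140 − 140 = 0 mg, so there is none to give.

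**Search for a saving clause.** None of 5.4.1, 5.4.3 or 5.4.4 contains an exception, footnote or ceiling for a 280 mg start. In the same 5.4.1 table, fludarabine resumes at its original dose with no amount printed, so that row does work for subjects whose fludarabine was reduced for renal function.

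**The case against.** **The benign reading is natural.** In 5.4.3 the relative words come first and 420 mg stands in parentheses, so the row can be read as describing the standard case. Sections 5.1, 5.2 and 12.1 also print 420 mg with no hepatic exception and plainly give way to 5.4.4. Many clinicians would restart at 280 mg. This has force, and it means a reader should not infer that the protocol unambiguously orders 420 mg. For class A subjects the wording contradicts itself. In 5.4.1 the order is reversed, with 420 mg as the instruction and original dose as the gloss. The second-occurrence and re-escalation lines there have no relative wording to fall back on.

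**Re-escalation is optional.** True, but nothing caps it for these subjects.

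**Few or no subjects are affected.** The trial plans 27 evaluable subjects. Section 4.2 also excludes raised bilirubin or AST/ALT (with exceptions), active hepatitis B or C, and conditions that the investigator thinks could "interfere with the absorption or metabolism of ibrutinib and fludarabine". The justification in 11.1.2 shows an intent to limit hepatic impairment, though it does not bar class A. Other rules cover CLL-related cytopenia (5.4.1 footnote), atrial fibrillation (5.4.2) and the permanent-discontinuation events in 5.5.3. All of this stands and keeps the point minor.

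**The exposure evidence is thin.** A reader might infer that 420 mg is intolerable in class A. The documents do not support that. The 2.7-fold AUC is a single-dose figure, 2.6.1 stresses variability between subjects, and 12.1 reports that no maximum tolerated dose was reached up to 1400 mg/day. The claim is only that 420 mg exceeds the dose the protocol mandates.

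**Conclusion.** The restart rules are wrong as written for subjects with Child-Pugh A impairment at enrollment. Severity is minor. The textual conflict is certain; that anyone would actually be dosed above 280 mg is not.

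The size is one of two failures, depending on the reading: a first restart 50% above the mandated start, or, in 5.4.1, no cut after a second cytopenia. These lie on different paths and should not be added together. The uncapped optional rise to 420 mg in 5.4.1 remains on both.

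The conclusion needs only that class A is eligible and that 280 mg is mandatory at the start, and the text gives both. It does not extend with the same force to subjects who become class A on study, because their 280 mg is a recommendation. Nor should a reader infer any effect on the two-stage designs in 9.3: power and type I error are unchanged.

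**What to change.** Add one footnote to both tables at the next amendment:

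> For subjects enrolled with Child-Pugh A impairment, 280 mg is the original and maximum ibrutinib dose. Do not restart or re-escalate above 280 mg while the impairment persists. The second-occurrence dose is 140 mg (medical team to confirm). In 5.4.1 the optional re-escalation is from 140 to 280 mg.

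The same footnote then governs liver-enzyme toxicity that 5.4.4 refers to 5.4.3. The third-occurrence action in 5.4.3 is a clinical choice and should be left to the medical team. The recommended on-study doses in 5.4.4 should stay recommendations and not become binding ceilings.

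**Cost.** Wording only, with no extra subjects or procedures. The downside is that these subjects may have fewer dose levels before discontinuation. A toxicity discontinuation within 6 cycles counts in the primary safety endpoint (9.1) and, if related to study drug, as non-response for efficacy (9.3). One such subject would be 1/27 = 3.7 percentage points.

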5.5 Holding of Study Drug Administration

5.5.1 Ibrutinib and Surgical Procedures:

Consider the benefit-risk of withholding ibrutinib for at least 3 to 7 days pre and post-surgery depending upon the type of surgery and the risk of bleeding.

5.5.2 Medically Necessary Conditions to Hold Study Drugs:

- If medically necessary reasons to hold ibrutinib occur during treatment (i.e. concurrent infection, impending workups for diagnostic and/or therapeutic purposes), ibrutinib can be held based on the study team's discretion.
- If medically necessary reasons to hold fludarabine occur during treatment (i.e. concurrent infection, emergence of autoimmune cytopenia, impending workups for diagnostic and/or therapeutic purposes), fludarabine can be delayed up to 2 cycles while continuing ibrutinib until the medical reasons to hold fludarabine resolve or return to baseline. If fludarabine is delayed beyond 2 cycles, fludarabine will be omitted and the patient will continue treatment with ibrutinib only.
- Supportive medications including allopurinol, and acyclovir (if indicated) intended to start at cycle 3 will be delayed until fludarabine starts or not given if fludarabine is omitted. Weekly labs intended for cycles 3 and 4 will be delayed until fludarabine starts or not performed if fludarabine is omitted.

5.5.3 Permanent discontinuation of study drug administration in case of treatment related adverse events:

- Serious or life threatening cardiac arrhythmias (grade 3 or 4)
- Severe infection (requiring vasopressor support > 24h, or intubation)
- Any grade 4 toxicity excluding readily reversible metabolic or laboratory abnormalities or hematologic toxicities
- Progressive disease as defined in section 7.3
- Pregnancy or unwillingness to use acceptable method of contraception

Patients who will not be able to receive further study drug administration will be followed for safety and after resolution of the event will continue to be followed at regular intervals and will undergo reassessment of disease as outlined in section 6 and 7.

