5.0 TREATMENT PLAN

5.1 Drug administration

Ibrutinib is an orally administered product. Study drug ibrutinib administration will take place in the outpatient facility of the NIH clinical center or at the patient's home. The drug dose is 420 mg PO daily. There is one specific dietary restriction to avoid grapefruit juice and Seville oranges due to CYP450 3A4 inhibition. Each dose of ibrutinib is to be taken with 8 ounces (approximately 240mL) of water. The capsule should be swallowed intact and subjects should not attempt to open the capsule or dissolve them in water. Ibrutinib will be given daily until disease progression or intolerable side effects.

Fludarabine is given as an intravenous infusion on cycle 3 and 4. Fludarabine administration will take place in the Clinical Center Day hospital. At the PI's discretion, select subjects may be admitted to the inpatient unit for the first few days of fludarabine infusion. Subjects will have a peripheral line placed. Per PI discretion, a central line may be placed in select patients. Fludarabine dose is 25 mg/m²/day on days 1-5 of cycles 3 and 4. Dosing will be based on actual weight for all patients. No dose adjustment is required based on age. In the event of renal impairment, dose reduction will be as follows;

- Creatinine clearance of 30-70 mL/min/1.73m² using the CKD-EPI equation with actual body weight: Fludarabine will be dose reduced by 20%.
- Creatinine clearance of ≤ 30 mL/min/1.73m² using the CKD-EPI equation with actual body weight: Fludarabine will be held at the discretion of the PI.

5.2 Therapy schedule: All cycles will be 28 (+/- 5) days long.

- Cycle 1 and 2: ibrutinib 420mg PO daily on day 1-28
- Cycle 3 and 4: ibrutinib 420mg PO daily on day 1-28, fludarabine 25mg/m²/day on day 1-5
- Cycle 5 and subsequent cycles up to C27: ibrutinib 420mg PO daily on day 1-28

5.3 Prophylactic Medications:

- Allopurinol 300mg PO once daily (or alternative agent in case the subject cannot tolerate allopurinol) during cycle 3 and 4 on days 1-7 for all subjects
- Sulfamethoxazole/trimethoprim DS PO once daily 3 times per week (or alternative agent in case of sulfa allergy) from cycle 1 to 9 and beyond at the discretion of the PI
- Acyclovir 800 mg PO twice daily or valacyclovir 500mg PO once daily at the discretion of the PI (not mandatory)

5.4 Holding and dose adjustments of study drug administration in the case of treatment related toxicity

5.4.1 Cytopenia:

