5.7 Permitted and Non Permitted Concomitant Medications (Investigators Brochure)

Patients may continue most medications they were prescribed prior to study enrollment for co-morbid conditions. No formal drug-drug interaction studies have been conducted therefore we ask patients to report all medications and over the counter drugs they are taking so we can monitor for any drug-drug interactions. Treatment for autoimmune cytopenias is permitted only during cycles with ibrutinib alone, but not during cycle 3 and 4 when fludarabine is added. Treatment for autoimmune cytopenias should not exceed 14 days at doses that do not exceed 100mg per day of prednisone or equivalent.

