6.2 On therapy evaluations (see schedule of events Appendix A)

From cycle 1 to 6 (+/- 5-day window):

Prior to each cycle, the following assessments will be completed. If the assessments have been already performed within 5 days of the study drug initiation as a part of screening or baseline evaluations, the study team can decide whether these assessments may or may not be repeated.

- Interval History
- ECOG performance status evaluation
- Physical exam
- Concomitant medication review
- CBC with differential
- Acute Care Panel (Na, K, Cl, CO₂, Creatinine, Glucose, and Urea Nitrogen)
- Mineral Panel (Phosphorus, Magnesium, Albumin, and Calcium)
- Total Protein, Uric Acid, and LDH
- Hepatic Panel (Alk Phosphatase, ALT, AST, Total Bilirubin, and Direct Bilirubin)
- Reticulocyte count
- Beta-2 microglobulin (B2M)
- Direct antiglobulin test (DAT)
- For females of childbearing potential, repeat pregnancy test
- Research blood (up to 80ml)

Additional blood draws, procedures, or imaging include (+/- 5-day window, except for CT scan and bone marrow biopsy):

Cycle 3&4

- Prior to Cycle 3 (within day -14 to 0): Lymphocyte phenotyping (T, B, NK), CT of neck/chest/abdomen/pelvis
- Cycle 3&4 Day 5 (+/- 5 days): Research blood (up to 80ml, optional)
- Cycle 3&4 Day 14, and 22 (+/- 5 days): CBC with differential (may be performed outside of NIH), research blood (up to 80ml) (if the blood was drawn at the NIH)

Cycle 5

- Cycle 5 Day 1 (+/-5-day window): Lymphocyte phenotyping (T, B, NK)

Others

- Up to 3 lymph node biopsies may be obtained for research at any time during therapy (optional, with at least 4 weeks between biopsies).

After cycle 6 (+/- 14-day window):

Following assessments will be done every 3 months while on therapy until disease progression or intolerable side effects.

- Interval History
- ECOG performance status evaluation

- Physical exam
- Concomitant medication review
- CBC with differential
- Acute Care Panel (Na, K, Cl, CO₂, Creatinine, Glucose, and Urea Nitrogen)
- Mineral Panel (Phosphorus, Magnesium, Albumin, and Calcium)
- Total Protein, Uric Acid, and LDH
- Hepatic Panel (Alk Phosphatase, ALT, AST, Total Bilirubin, and Direct Bilirubin)
- Reticulocyte count
- Beta-2 microglobulin (B2M)
- Direct antiglobulin test (DAT)
- For females of childbearing potential, repeat pregnancy test
- Research blood (up to 80ml)

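### For autoimmune hemolysis with hemoglobin below 11 g/dL at the start of cycle 3 or 4, section 5.4.1 omits fludarabine while section 5.5.2 lets it be delayed and resumed, and the plan does not say which governs

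*Combined protocol and SAP*

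**What the plan says.** Three sections of the protocol bear on an autoimmune cytopenia around the fludarabine cycles.

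- **Section 5.4.1 (cytopenia table).** Conditions are judged at the start of the cycle. For fludarabine in cycles 3 and 4, the row "HGB <11 g/dL with indications of autoimmune hemolysis" has omission as its only action. The neutrophil and platelet rows defer first, resume on recovery, and end with "If count recovery does not occur in 8 weeks, omit fludarabine".
- **Section 5.5.2 (medically necessary holds).** Reasons to hold fludarabine include "emergence of autoimmune cytopenia, impending workups for diagnostic and/or therapeutic purposes), fludarabine can be delayed up to 2 cycles while continuing ibrutinib". The delay lasts until the reason resolves or is back at baseline. Beyond 2 cycles fludarabine is omitted and the patient stays on ibrutinib alone.
- **Section 5.7 (concomitant medications).** "Treatment for autoimmune cytopenias is permitted only during cycles with ibrutinib alone, but not during cycle 3 and 4 when fludarabine is added". A further sentence limits such treatment to 14 days and 100 mg per day of prednisone or equivalent.

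Section 4.2 excludes "Active autoimmune hemolytic anemia or thrombocytopenia" at entry, so the question concerns new onset on study.

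**The concern.** Hemolysis with hemoglobin below 11 g/dL is an autoimmune cytopenia. If it is present when cycle 3 or 4 is due to start, the patient satisfies the triggers of both 5.4.1 and 5.5.2. One section withholds the drug. The other allows a pause and a restart. What is at stake is whether a patient with new autoimmune hemolysis is exposed to fludarabine again, in a trial that section 10.0 describes as the first to combine these two drugs.

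The case can surface at a routine visit. Section 6.2 schedules blood count, reticulocytes, LDH, bilirubin and direct antiglobulin test before each of cycles 1 to 6.

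Section 5.7 raises a second question. Fludarabine is given only on days 1 to 5, but the restriction on treating an autoimmune cytopenia is worded by cycle. It therefore continues after the last infusion.

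**Working it through.** The plan states no figure to reproduce. The check is a comparison of the text, with a little arithmetic on days and dose.

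**1. Does one patient meet both rules?**

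- Time: 5.4.1 applies at the start of cycle 3 or 4. 5.5.2 applies at any time during treatment, so it includes that moment.
- Trigger: 5.4.1 needs hemoglobin below 11 g/dL with signs of autoimmune hemolysis. 5.5.2 needs an emerging autoimmune cytopenia and has no hemoglobin limit or exception for hemolysis.
- Action: omit under 5.4.1; delay, then resume, under 5.5.2.
- Precedence: neither section mentions the other. The footnote to the 5.4.1 table relaxes delay and reduction when the cytopenia is attributed to CLL, and does not rank the sections.

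The overlap is exactly this patient. Immune thrombocytopenia, hemolysis with hemoglobin of 11 g/dL or more, and onset after the cycle has started meet only 5.5.2.

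**2. Is omission just another word for delay?** No. The other fludarabine rows of the same table use both terms, with omission as the last step after 8 weeks. By section 5.2, "All cycles will be 28 (+/- 5) days long". The 5.5.2 limit is thus 2 × 28 = 56 days = 8 weeks, or 2 × 23 = 46 to 2 × 33 = 66 days with the window. At the nominal length this equals the deferral allowed in the neutrophil and platelet rows. Applying 5.5.2 to hemolysis would give it the deferral that the 5.4.1 row leaves out.

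**3. Dose at stake.** From section 5.1, 25 mg/m² per day for 5 days:

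- one course: 25 × 5 = 125 mg/m²;
- both courses: 2 × 125 = 250 mg/m².

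An event at the start of cycle 4 puts 125 mg/m² at stake. At the start of cycle 3 it is 250 mg/m² if omission covers both courses, and 125 mg/m² if it covers that cycle only. These are full doses, before any reduction.

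**4. Length of the 5.7 restriction after the last infusion.**

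- 28-day cycle: 28 − 5 = 23 days (days 6 to 28).
- Shortest cycle: 23 − 5 = 18 days. Longest: 33 − 5 = 28 days.

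For a cycle 3 event this assumes that cycle 4 fludarabine is then held or omitted; otherwise cycle 4 is restricted too. Section 6.2 schedules counts inside this period: "Cycle 3&4 Day 14, and 22 (+/- 5 days): CBC with differential".

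**The case against.** The best answer on the main point is that the specific rule displaces the general one. 5.5.2 is permissive and 5.4.1 is directive, so a physician who omits fludarabine breaches neither section, and 5.5.2 keeps the cases that 5.4.1 does not reach. This is a natural reading, and the fix adopts it. But the plan does not state it, and 5.5.2 is more than a general clause. It lists autoimmune cytopenia for fludarabine and not for ibrutinib, and it supplies its own restart condition, time limit and omission rule. A physician who delays and resumes can point to it.

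Section 5.4 is headed as dealing with treatment-related toxicity, so attribution might also separate the two sections. That narrows the overlap without removing it, since 5.5.2 is not limited by cause and a treatment-related hemolysis meets both.

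It can also be said that the scope of omission is largely answered, because 5.5.2 pairs omission with continuing on ibrutinib only. That stands. What remains is to say so in the 5.4.1 row.

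On 5.7, a reader might infer that the restriction is a mistake because no infusion is left to hold after day 5. The documents do not support that. Lymphodepletion outlasts the infusions, and T-cell recovery is central to the rationale in section 2.7.1. Section 6.2 also has a readout soon afterwards: "Cycle 5 Day 1 (+/-5-day window): Lymphocyte phenotyping (T, B, NK". Avoiding corticosteroids in those weeks may be deliberate, although no reason is given. Nor is the patient left without care. Transfusion remains available under 5.6.1, and non-protocol treatment is possible at the cost of leaving the study (section 9.7).

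**Conclusion.** The conflict between 5.4.1 and 5.5.2 is real and confined to hemolysis with hemoglobin below 11 g/dL at the start of cycle 3 or 4. Depending on the section followed, such a patient receives no further fludarabine or resumes it after a delay of up to 56 days (46 to 66). It should be corrected because it concerns patient safety and the correction is small.

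The 5.7 restriction is a query, not an error: on a literal reading it lasts 23 days after the last infusion (18 to 28).

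Two wider inferences are not supported. One is that many patients are affected. Section 2.2 gives 37% for autoimmune hemolytic anemia and 2–4% for immune thrombocytopenia, but as complications of CLL, not as onset rates over two cycles in patients free of active disease at entry. The documents give no such rate, so the number cannot be calculated; it is likely to be small. The other is that the primary analysis is compromised. Nothing here shows an effect on the complete response rate, the power or the error rates.

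**What to change.** - **5.5.2:** after the mention of autoimmune cytopenia, add: *except autoimmune hemolysis with HGB <11 g/dL present at the start of cycle 3 or 4 (including the start of a delayed fludarabine cycle), for which fludarabine is omitted per 5.4.1*.
- **5.4.1, hemolysis row:** change the action to *Omit all remaining fludarabine and continue ibrutinib only*, in line with how 5.5.2 uses the term.
- **Left as they are:** immune thrombocytopenia, hemolysis with hemoglobin of 11 g/dL or more, and onset after cycle start stay under 5.5.2 until the next start-of-cycle check.
- **5.7 (query):** the investigator either confirms that the restriction is intended and gives the reason, or permits treatment once no more fludarabine will be given in that cycle. In the second case fludarabine should restart on the existing 5.5.2 condition (resolution or return to baseline), so that no second standard is created.

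**Cost.** The edits are sentence-level but need an amendment, with company approval and IRB approval under section 10.6. No visits, tests or patients are added. The few patients affected lose the option of resuming fludarabine after recovery. If 5.7 is loosened, some would receive corticosteroids soon after fludarabine, with added infection risk and possible influence on the cycle 5 lymphocyte phenotyping. That trade-off is clinical and is for the investigator to decide.
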